9.6.6.3 Serious Adverse Events (SAEs) and Unexpected Adverse Device Effects (UADEs)

A SAE is defined as any unfavorable medical occurrence that meets any of the following:

1. Results in death.
2. Is life-threatening: “Life-threatening” refers to an event in which the subject was at risk of death at the time of the event; it does not refer to an event, which hypothetically might have caused death if it were more severe.
3. Requires inpatient hospitalization or prolongation of existing hospitalization: Planned and routine hospital admissions for pre-existing conditions are not considered SAEs and do not require reporting as an AE unless the condition has worsened beyond what would reasonably be expected for that subject. If a subject experiences an additional AE that prolongs a pre-planned hospitalization this is considered to be an SAE and should be reported as an SAE. Pre-planned admissions must be recorded in the subject’s source documentation.
4. Results in persistent or significant disability/incapacity.
5. Is a congenital anomaly or birth defect.
6. Is an important medical event: Important medical events that may not be immediately life-threatening or result in death or hospitalization but may jeopardize the subject or may require

intervention to prevent one of the other outcomes listed above should usually be considered serious.

A **UADE** is defined as any device-related AE that meets any of the following:

1. Is not identified in nature, severity or frequency in current literature on the product.
2. Is life threatening, even if temporary in nature.
3. Results in permanent impairment of a body function or permanent damage to a body structure.
4. Necessitates medical or surgical intervention to preclude permanent impairment of a body function or permanent damage to a body structure.
5. Any device malfunction that would be likely to cause or contribute to a death or serious injury if the malfunction were to recur.

9.6.6.4 Causality Assessment

The TI's assessment of an AE's relationship to the study device is part of the documentation process, but it is not a factor in determining what is or is not reported in the study. If there is any doubt as to whether a clinical observation is an AE, the event will be reported. The TI will assign the causality assessment according to his/her clinical experience and the subject's description of the event. The Sponsor will be responsible for the final causality judgment. The causal relationship should be classified according to the following criteria (not all variables need to be present to be indicative of relationship to the device):

Definitely related:

- The temporal sequence of AE onset relative to injection of study device is reasonable.
- The AE is more likely explained by the study device or procedure than by another cause.
- The AE shows a pattern consistent with previous knowledge of the study device.

Probably related:

- The temporal sequence of AE onset relative to injection of study device is reasonable.
- The AE is more likely explained by the study device or procedure than by another cause.

Possibly related:

- The temporal sequence of AE onset relative to injection of study device is reasonable.
- The AE could have been due to another equally likely cause.

Probably not related:

- There is another more likely cause of the AE.

Definitely not related:

- The temporal sequence of AE onset relative to injection of study device is not reasonable.
- There is another obvious cause of the AE.

9.6.6.5 Severity Assessment

For events reported on the AE eCRF, the TI will determine the severity classification based on his/her clinical experience and by using the following definitions of severity (note: a "severe" AE is not the same as a SAE):

- Mild: Symptoms are barely noticeable or do not make the subject uncomfortable. The AE does not influence performance or functioning. Prescription drugs are not ordinarily needed for relief of symptom(s).
- Moderate: Symptoms are of sufficient severity to make the subject uncomfortable. Performance of daily activities is influenced. Treatment of symptom(s) with prescription drugs or therapies may be needed.
- Severe: Symptoms are of sufficient severity to cause the subject severe discomfort. Performance of daily activities is compromised. Treatment for symptom(s) with prescription drugs or therapies may be needed.

The maximal severity for the AE will be recorded, even if the AE presented as being less severe at some point during the event.

9.6.7 Adverse Event Reporting

9.6.7.1 All Adverse Events

All AEs, whether serious or not, will be recorded from the time of informed consent until the last study visit, or until 1 month following the last study treatment. The TI will assess all AEs and record details of seriousness, severity, duration, and action taken with study device, and relationship to the study device. The Sponsor is responsible for reporting AEs to the relevant governing authorities in the time frame applicable according to international and local law.

9.6.7.2 Serious Adverse Events (SAEs) and Unexpected Adverse Device Effects (UADEs)

All SAEs and UADEs that occur after the time of informed consent through to 7 days after a subject's completion of study participation, or within 1 month following the last study treatment, must be reported [REDACTED] within 24 hours of awareness.

- Obtain and maintain all pertinent medical records, information, and medical judgments from colleagues who assisted in the treatment and follow-up of the subject.
- Provide [REDACTED] a complete, written case history, including copies of supporting reports (e.g., progress notes, laboratory reports) and a statement as to whether the event was or was not related to the use of the study device.
- [REDACTED] notify the governing IRB of the SAE or UADE in accordance with the requirements of SAE reporting stipulated by the governing IRB.

Reporting Timelines

[REDACTED] **UADEs:** The site must report the UADE [REDACTED] within 24 hours of becoming aware of the event. Within 24 hours of receiving the UADE report from the site [REDACTED] [REDACTED] must report the UADE to the Sponsor. As required by 21 CFR 812.46 (US) and Subsection 59(1) of the Medical Device Regulations (SOR/98-282) (Canada), the Sponsor

must investigate the UADE and report the results to the FDA, Health Canada and IRB within 10 working days[†] of receiving the report [REDACTED]

- **SAEs:** The site must report the SAE [REDACTED] within 24 hours of becoming aware of the event. Within 24 hours of receiving the SAE report from the site, [REDACTED] should report the SAE to the Sponsor. The Medical Monitor will investigate the SAE. SAEs will be reported to the IRB as per the regulations of the IRB. SAEs will be reported to FDA in study annual and final reports.

[REDACTED]

Study Hold Due to UADEs

- If the Medical Monitor determines that an UADE(s) presents an unreasonable risk to subjects, the Sponsor shall put on hold all investigation or parts of investigations presenting that risk as soon as possible. The study hold shall occur no later than 5 working days after the Sponsor makes this determination and not later than 15 working days after the Sponsor first received notice of the effect. The Sponsor will not resume an on hold investigation without IRB, Health Canada and FDA approval.

9.6.7.3 Pregnancy

Pregnancy is not considered an SAE or AE. The site will inform [REDACTED] immediately of any case of pregnancy and collect information on any subject who becomes pregnant during the study using the *Unexpected Problems Report Form*

Subjects who become pregnant will not receive further treatments with the study device(s), but will continue to be followed up for scheduled efficacy and safety assessments for the duration of the study. All pregnancies should be followed to term and the outcome reported [REDACTED] to determine the outcome of pregnancy.

10 SUBJECT COMPLETION / WITHDRAWAL

[figure not shown]
10.1 Completion

A subject will be considered to have completed the study if he or she has completed all the assessments or has experienced an event that precludes further participation in the study.

10.2 Discontinuation of Treatment

A subject will be discontinued from further applications of the study devices if they become pregnant; however, they will continue all other assessments as per protocol.

10.3 Withdrawal

The reason and date of withdrawal must be noted on the eCRF. If the reason for withdrawal is an AE or an abnormal laboratory test result, monitoring will continue until resolution or until

an appropriate medical judgment concerning the cause or importance has been made. The specific event or test result(s) must be recorded on the eCRF.

11 STATISTICAL METHODS

11.1 Primary Endpoint

The primary endpoint will be a co-primary endpoint. A responder will be defined as a subject who has a ≥ 1 -grade improvement on the PR-SRS as assessed by the BLE at Week 8 after initial or touch-up treatment, compared with the pre-treatment assessment (baseline) by the BLE. Only data from the first 8-week phase will be taken into account. The No-Treatment control group after treatment will not be pooled for the primary endpoint.

The effectiveness of TEOSYAL® RHA Redensity will be demonstrated if:

- The responder rate for subjects treated with TEOSYAL® RHA Redensity is statistically superior to the responder rate for the No-Treatment control, and;
- The responder rate for subjects treated with TEOSYAL® RHA Redensity is $\geq 70\%$, and;
- The difference between the responder rate for subjects treated with TEOSYAL® RHA Redensity and the No-Treatment group is ≥ 50 points.

11.2 Secondary Endpoints

For the Secondary Endpoints, like for the Primary Endpoint, only data from the first 8 week phase will be taken into account, and will compare TEOSYAL® RHA Redensity to No-Treatment (the No-Treatment control group after treatment will not be pooled for the secondary endpoints):

- FACE-Q at Week 4 and Week 8 after initial or touch-up treatment.
- Proportion of subjects with a Global Aesthetic “improved” or “much improved”, as assessed by subject at Week 8 after initial or touch-up treatment, using the 5-grade Global Aesthetic Improvement (GAI) scale.
- Proportion of subjects with a Global Aesthetic “improved” or “much improved”, as assessed by BLE at Week 8 after initial or touch-up treatment, using the 5-grade Global Aesthetic Improvement (GAI) scale.
- Proportion of subjects “satisfied” or “very satisfied” at Week 8 after initial or touch-up treatment, using the 5-point scale assessing subjects’ satisfaction with study treatment.

11.3 Exploratory Endpoints

For the following Exploratory Endpoints, like for the Primary Endpoint, only data from the first 8 week phase will be taken into account and will compare TEOSYAL® RHA Redensity to No-Treatment (the No-Treatment control group after treatment will not be pooled for these exploratory endpoints):

- Proportion of subjects with ≥ 1 -grade improvement from pre-treatment on the PR-SRS as assessed by the Treating Investigator, at Week 4 and Week 8 after initial or touch-up treatment, compared with the pre-treatment assessment (baseline) by the Treating Investigator.
- Proportion of subjects with a Global Aesthetic “improved” or “much improved”, as assessed by Treating Investigator at Week 4 and Week 8 after initial or touch-up treatment, using the 5-grade Global Aesthetic Improvement (GAI) scale.

- Proportion of subjects with ≥ 1 -grade improvement from pre-treatment of dynamic perioral rhytids on the 1-4 Modified Glogau classification of wrinkling as assessed by the BLE at Week 8 after initial or touch-up treatment, compared with the pre-treatment assessment (baseline) by the BLE.
- Proportion of subjects with ≥ 1 -grade improvement from pre-treatment of dynamic perioral rhytids on the 1-4 Modified Glogau classification of wrinkling as assessed by the Treating Investigator at Week 4 and Week 8 after initial or touch-up treatment, compared with the pre-treatment assessment (baseline) by the Treating Investigator.
- Proportion of subjects with ≥ 1 -grade improvement from pre-treatment on the PR-SRS, as evaluated by the Independent Photographic Reviewers (IPR) at Week 8 after initial or touch-up treatment, compared with the pre-treatment assessment (baseline) by the IPR. For a given subject to be considered a responder, at least 2 of the 3 readers must have confirmed a 1-point improvement for that subject.

For the following Exploratory Endpoints, unlike for the Primary and Secondary Endpoints, data from the TEOSYAL® RHA Redensity group and from the No-Treatment control group after treatment will be pooled (if deemed comparable).

- Proportion of subjects with ≥ 1 -grade improvement of their dynamic perioral rhytids on the 1-4 Modified Glogau classification of wrinkling as assessed by the BLE at Week 8, 12, 16, 24, 36, and 52 after initial or touch-up treatment, compared with the pre-treatment assessment (baseline) by the BLE.
- Proportion of subjects with ≥ 1 -grade improvement of dynamic perioral rhytids on the 1-4 Modified Glogau classification of wrinkling as assessed by the Treating Investigator at Week 4, 8, 12, 16, 24, 36, and 52 after initial or touch-up treatment, compared with the pre-treatment assessment (baseline) by the Treating Investigator.
- Subject satisfaction at Weeks 4, 8, 12, 16, 24, 36, and 52 after initial or touch-up treatment, using the 5-point scale assessing subjects' satisfaction with study treatment.
- FACE-Q at Week 4, 8, 12, 16, 24, 36, and 52 after initial or touch-up treatment
- Proportion of subjects with a ≥ 1 -grade improvement based on the PR-SRS assessed by the Treating Investigator at Weeks 4, 8, 12, 16, 24, 36, and 52 after initial or touch-up treatment, compared with the pre-treatment assessment (baseline) by the Treating Investigator.
- Proportion of subjects with a ≥ 1 -grade improvement based on the PR-SRS assessed by the BLE at Weeks 8, 12, 16, 24, 36, and 52 after initial or touch-up treatment, compared with the pre-treatment assessment (baseline) by the BLE.
- Proportion of subjects with a ≥ 1 -grade improvement, based on the PR-SRS as evaluated by the Independent Photographic Reviewers (IPR) at Week 8, 12, 16, 24, 36, and 52 after initial or touch-up treatment, compared with the pre-treatment assessment (baseline) by the IPR. For a given subject to be considered a responder, at least 2 of the 3 readers must have confirmed a 1-point improvement for that subject
- Proportion of subjects with a Global Aesthetic "improved" or "much improved", as assessed by subjects at Week 4, 8, 12, 16, 24, 36, and 52 after initial or touch-up treatment, using the 5-grade Global Aesthetic Improvement (GAI) scale.

- Proportion of subjects with a Global Aesthetic “improved” or “much improved”, as assessed by Treating Investigators at Week 4, 8, 12, 16, 24, 36, and 52 after initial or touch-up treatment, using the 5-grade Global Aesthetic Improvement (GAI) scale.
- Proportion of subjects with a Global Aesthetic “improved” or “much improved”, as assessed by BLE at Week 8, 12, 16, 24, 36, and 52 after initial or touch-up treatment, using the 5-grade Global Aesthetic Improvement (GAI) scale.
- Proportion of subjects with a natural look ≥ 7 , and proportion of subjects with a natural feel ≥ 7 , both assessed by subjects at Week 4, 8, 12, 16, 24, 36, and 52 after initial or touch-up treatment, using a 11-point scale.

11.4 Analysis Populations

Three subject analysis populations are defined: Per Protocol (PP) Population, Intent-to-Treat (ITT) Population, and Safety (SAFT) Population. All analysis populations will be defined and determined prior to unblinding and database closure for the final analysis.

11.4.1 Intent-to-Treat (ITT) Population

[REDACTED]

11.4.2 Per Protocol (PP) Population

[REDACTED]

11.4.3 Safety (SAFT) Population

The SAFT Population will consist of all study subjects that were randomized and received at least one treatment with the study device.

11.5 Sample Size Considerations

[REDACTED]

The study will ensure that enrolled subjects are representative of U.S. population ethnicity and will be comprised of at least 25% subjects of Fitzpatrick skin IV to VI. In order to be able to detect a sufficient AE rate (i.e., maximum 2.5% in the sub-population of subjects of Fitzpatrick skin type IV to VI), the number of subjects must be increased beyond that required for achieving statistical power for the primary efficacy outcome; specifically:

[REDACTED]

11.6 General Considerations

Data will be listed by treatment group and subject number. The safety and efficacy data will be summarized by treatment allocation. Descriptive statistics will consist of values, tables, mean, standard deviation, minimum and maximum for continuous variables, and frequency and percent for discrete variables.

A full description of the statistical methods planned for this study will be provided in the Statistical Analysis Plan (SAP). All programs for data output and analyses will be written in SAS version 9.3 or higher (SAS Institute, Inc., Cary, NC).

Missing Values

For subjects lost-to-follow-up (LTFU), or not present at a visit, missing data will be imputed using last observation carried forward (LOCF) for the primary endpoint (PR-SRS, ITT population). Various statistical procedures to confirm the impact of missing data (e.g., Tipping Point Analysis) will be detailed in the Statistical Analysis Plan. No imputations will be performed for secondary endpoints; analyses will utilize available data as observed.

Discontinuation and Drop-Outs

Dropouts will not be replaced. All available data from dropouts will be included in the ITT analysis. Subject disposition will be summarizing the number of subjects enrolled in the study and those that discontinued the study and their reason.

Interim Analysis

[figure not shown]
[figure not shown]
[figure not shown]
There will be no interim efficacy analysis.

Poolability Between Countries

Due to the potential impact on safety and effectiveness, the variation in data across baseline demographics will be accounted, and heterogeneity across the two countries (US and Canada) will be investigated to establish if the data for safety and effectiveness can be combined.

To assess the homogeneity of the baseline characteristics across the two countries, and to determine if data from both countries could be pooled, statistical hypothesis tests will be performed with their null hypotheses as the absence of difference between US and Canada. All observed two-sided p-value must be >0.05 to pool data from the two countries. If the two-sided p-value is less or equal to 0.05, then, data collected from subjects of both countries will not be pooled. Percentages of each characteristic of the demographics will be compared using a Fischer's Exact test, and continuous data will be compared using a Student t test. The full details will be provided in the Statistical Analysis Plan.

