Study Duration	52 to 58 weeks for subjects randomized to TEOSYAL® RHA Redensity treatment group, and 60 to 66 weeks for subjects randomized to the “No-Treatment” control group	Number of Subjects	At least 200 subjects, 150 treated and 50 No-Treatment controls
Treatment Groups	
Subjects will be randomized (3:1 ratio) to one of the following groups:
 
 • TEOSYAL® RHA Redensity • No-Treatment control 		

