4 OVERVIEW OF STUDY DESIGN

4.1 Study Design

This is a randomized, blinded, No-Treatment control, multicenter, prospective clinical study, to identify whether TEOSYAL® RHA Redensity is more effective than No-Treatment in the correction of moderate to severe perioral rhytids at Week 8 after initial or touch-up treatment.

The **Treating Investigator** (TI) will evaluate subjects for eligibility of the subject for the study. The **Blinded Live Evaluator** (BLE) at screening will evaluate the subject's perioral rhytids severity using the Perioral Rhytids Severity Rating Scale (PR-SRS) in order to confirm eligibility and to establish a pre-treatment score. This will be done independently of the TI, and exact concordance between the BLE and the TI is not necessary.

Enrolled subjects will be randomized to either the TEOSYAL® RHA Redensity treatment group or the “No-Treatment” control group. The TI will administer study device, and if necessary, subjects will receive a touch-up treatment 14 days following the initial treatment to optimize the results. The TI will conduct safety and effectiveness evaluations at study subject visits, which will occur at Week 4, 8, 12, 16, 24, 36, and 52 after initial or touch-up treatment, and 4 weeks after a repeat treatment.

The BLE will conduct assessments of efficacy during the trial, including assessment of the primary endpoint at Week 8 after initial or touch up treatment. The BLE will conduct effectiveness evaluations at Week 8, 12, 16, 24, 36, and 52 after initial or touch-up treatment.

Subjects will be followed for 52 weeks from initial or touch up treatment, at which point they will be offered a repeat treatment (provided that the TI deems the treatment to be appropriate, and if the subject agrees). The subject will then be followed for an additional 4 weeks after the treatment before exiting the study.

[figure not shown]
Should a subject return to his/her pre-treatment PR-SRS level before Week 52, as assessed by the TI, he/she will be eligible to receive an early repeat treatment (provided that the TI deems the treatment to be appropriate, and if the subject agrees) at Week 12, or Week 16, or Week 24, or Week 36 after initial or touch-up treatment. .

Subjects randomized to the “No-Treatment” control group will receive their first treatment after the primary endpoint evaluation (8 weeks after randomization) and will then follow the same schedule as the initial treatment group.

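### Does LOCF for the primary endpoint need replacing because it turns every missing Week 8 rating into a non-response?

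*Protocol*

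**What the plan says.** Protocol 11.6 (General Considerations, Missing Values) sets the rule: "missing data will be imputed using last observation carried forward (LOCF) for the primary endpoint (PR-SRS, ITT population". It does not name the rater whose value is carried. It continues: "Various statistical procedures to confirm the impact of missing data (e.g., Tipping Point Analysis) will be detailed in the Statistical Analysis Plan".

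Protocol 11.1 and SAP 9.1.1 define response as an improvement of at least one PR-SRS grade on the BLE's Week 8 rating relative to the BLE's own baseline, and add: "Only data from the first 8-week phase will be taken into account". Success requires statistical superiority, a treated responder rate of at least 70%, and a difference of at least 50 points.

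Protocol 4.1 and SAP 2.1 give the BLE a screening rating and then this schedule: "The BLE will conduct effectiveness evaluations at Week 8, 12, 16, 24, 36, and 52 after initial or touch-up treatment". The treating investigator (TI) is also scheduled at Week 4, and Protocol 11.3 lists response "on the PR-SRS as assessed by the Treating Investigator, at Week 4 and Week 8 after initial or touch-up treatment" among the between-arm exploratory endpoints.

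SAP section 1 says that the SAP prevails where the documents differ. Its table of contents lists 9.3.4, Missing Values, but the text of that section and the ITT definition are not visible in the public copy.

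**The concern.** The name LOCF suggests that some post-treatment information is carried forward. Here there is none to carry. With no BLE rating between screening and Week 8, the last BLE observation is the baseline, so the change is zero and the subject is a non-responder. In effect the rule is missing = non-responder, although the protocol does not call it that.

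Two of the three success criteria are fixed thresholds, so missed visits alone could pull a treated rate that is truly above 70% below the line. The treated arm may also have slightly longer to drop out. Under the plan, if necessary, "subjects will receive a touch-up treatment 14 days following the initial treatment to optimize the results", which puts that subject's primary rating about 10 weeks after first treatment. Controls "will receive their first treatment after the primary endpoint evaluation (8 weeks after randomization"), so theirs falls at 8 weeks. Meanwhile the TI's Week 4 score, collected in both arms, goes unused.

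**Working it through.** **Plan's own figure.** The one visible sample-size calculation (Protocol Synopsis) reproduces: 160 / (1 − 0.20) = 200. Split 3:1, this gives 150 treated and 50 control.

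**Share missing at Week 8 (m).** The documents do not give it. The Synopsis assumes 20% dropout over the whole study, with durations of "52 to 58 weeks for subjects randomized to TEOSYAL® RHA Redensity treatment group, and 60 to 66 weeks for subjects randomized to the" control group. Spreading dropout evenly over time (an assumption):

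- Treated: 0.20 × 8/58 = 2.8% to 0.20 × 10/52 = 3.8%. The upper end pairs a touch-up with the shortest follow-up. With the longest follow-up it is 0.20 × 10/58 = 3.4%.
- Control: 0.20 × 8/66 = 2.4% to 0.20 × 8/60 = 2.7%.

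So about 3% is the central case. The 5% and 10% cases below are stress cases that no figure in the documents supports.

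**Effect on the thresholds.** Let pt and pc be the true response rates. With missingness unrelated to response, the analysed rates are pt(1 − m) and pc(1 − m). To reach 70% and 50 points, assessed subjects must show 70/(1 − m) and 50/(1 − m):

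| m | treated rate needed | difference needed |
|---|---|---|
| 3% | 72.2% | 51.5 |
| 5% | 73.7% | 52.6 |
| 10% | 77.8% | 55.6 |

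**Chance of meeting both numeric cut-offs as point estimates.** This is the exact probability that X ≥ 105 and X − 3Y ≥ 75, where X ~ Bin(150, pt(1 − m)) and Y ~ Bin(50, pc(1 − m)). The response rates are assumptions.

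| pt, pc | m = 0 | 3% | 5% | 10% |
|---|---|---|---|---|
| 85%, 10% | 100 | 100 | 99.9 | 97.3 |
| 80%, 10% | 99.8 | 98.8 | 96.2 | 73.9 |
| 75%, 10% | 93.0 | 80.1 | 66.8 | 28.7 |
| 80%, 20% | 93.9 | 89.5 | 85.0 | 62.3 |
| 75%, 20% | 76.4 | 63.5 | 52.3 | 22.6 |

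With arm-specific shares (2.8% or 3.8% treated, 2.4% control) and pc = 10%, the chance is 98.9% or 97.9% at pt = 80%, and 81.4% or 74.8% at pt = 75%.

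**Direction.** On the 70% criterion the rule can only lower the treated rate. On the difference it helps the device only if mc × pc > mt × pt, where mt and mc are the treated and control missing shares. That means mc/mt > pt/pc. At 80% against 10%, control missingness would have to exceed 8 times treated missingness.

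**What the replacement would do.** The alternative is multiple imputation of Week 8 BLE response within arm, with TI Week 4 response as predictor. Take a device that should fail, with a true treated rate of 68%. In a simulation of 4,000 runs with BLE non-responders twice as likely to miss Week 8 (assumed), the chance of passing both cut-offs was:

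| | m = 3% | m = 10% |
|---|---|---|
| Full data | 33.4% | 33.4% |
| Multiple imputation | 35.0% | 45.9% |
| Missing = non-responder | 20.4% | 3.9% |

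The full-data figure agrees with the exact value of 33.2% (pc = 10%). At 3% missing, imputation roughly restores what full data would give. At 10% it passes a failing device 45.9 − 33.4 = 12.5 points more often than full data would. The present rule errs the other way in both columns.

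**The case for a change.** The strongest case for change is that a conservative rule should be chosen and named, and here it arises as a by-product of the BLE schedule. The cost is real when the true rate is close to the cut-off: at 75% against 10%, 3% missingness takes 93.0 − 80.1 = 12.9 points off the chance of success. A tipping-point analysis tests robustness but does not alter the primary estimate that decides the outcome. Imputation would need no new data.

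The mechanism and the arithmetic stand. The case for replacing the rule does not:

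- The loss is a missed success, borne by the sponsor that chose the rule. It does not weaken a positive result.
- Nothing visible shows that the trial was planned near 70%, since the efficacy power text is redacted.
- The table assumes missingness unrelated to response. If non-responders are the ones who stay away, less is lost: at a true 68% the rule passes 20.4% at 3% missing under outcome-dependent missingness, against 16.8% under random missingness.
- Imputation would rest on a missing-at-random model for a handful of subjects and use an unblinded rater's score to fill a blinded endpoint. If the primary test is Fisher's exact, the general rule for 2×2 tables in SAP 9.3.1, it would also need a different test that can be pooled over imputations.

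What remains is wording: the protocol names neither the rater nor the effective rule. An analyst working from an endpoint defined wholly on BLE ratings would carry the BLE value, and SAP 9.3.4 may say so. The protocol already defers the sensitivity analyses to the SAP.

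**Conclusion.** The observation is correct on the visible text: LOCF here means missing = non-responder in both arms. No change follows. The rule is conservative on the 70% criterion, and on the 50-point criterion unless control missingness exceeds treated missingness by more than the ratio of the response rates. At the roughly 3% Week 8 missingness implied by evenly spread dropout, it costs 99.8 − 98.8 = 1.0 point of success chance at 80% against 10% and nothing visible at 85%. With control response at 20% and treated at 80% it costs 93.9 − 89.5 = 4.4 points. It becomes material only when the true treated rate is within about 5 points of 70%. Replacing it would trade a transparent, cautious rule for a model-based one that can favour the device, which is a matter of preference and not a correction.

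This rests on assumed response rates, on even dropout over time, and on SAP 9.3.4 and the ITT definition not departing from the protocol's rule. If SAP 9.3.4 does set a different rule, it prevails and the question does not arise in this form.
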